## RESEARCH STRATEGY

### A.1. SIGNIFICANCE.

**Adolescent alcohol and drug use (ADU) is a significant public health challenge in SSA.** About 41.6% of adolescents in SSA have used at least one psychoactive agent. Alcohol is the most commonly used drug; one third of adolescents have used alcohol in their lifetime, 22.5 million are current drinkers, and over 50% engage in heavy episodic drinking. Alcohol use nearly doubles during the transition to adulthood, from 21.4% of adolescents aged 16-19 to 34.1% of young adults aged 20-24 years. Uganda, one of the poorest countries in SSA, has the second highest rate of per capita alcohol consumption in SSA (15.1 liters of pure alcohol vs regional average of 6.2 liters of pure alcohol). Over 30% of Ugandan adolescents and youth have used alcohol and about 20% misuse alcohol. These estimates reach even greater magnitudes in the country's fishing villages – a key HIV vulnerable population- where ADU is normative. A few studies have assessed ADU among AYLHIV. A study conducted in Rwanda found that 61% of AYLHIV receiving medication from a clinic had drunk alcohol within 6 hours prior to having sex. In South Africa, a prior study found that 53.8% of the male AYLHIV and 5% of female AYLHIV had ever used drugs. In Uganda, a recent cross-sectional study of 479 adolescents aged 12 – 17 years found that 5.9% reported use of at least one psychoactive substance, including alcohol (4.3%), marijuana (2.1%) and other drugs (2.1%) such as cocaine, glue and heroine. ADU is a key driver of new HIV infections and poor HIV care outcomes in SSA. It is associated with HIV risk behaviors such as increased sexual risk-taking, unprotected sex, early sexual debut, an increased number of sexual partners, resulting in transmission of HIV. ADU is also associated with sub-optimal mental health e.g. depression and suicidal ideation. Among AYLHIV, ADU impedes adherence to anti-retroviral therapy (ART), retention in care, and viral suppression. Among HIV-infected adults, ADU have been shown to increase susceptibility to AIDS mortality, even among HIV virally suppressed and medication adherent persons.

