## B. INNOVATION.

The proposed study innovates in the following ways: (1) **We focus on older adolescents and young adults in a high-risk environment to elucidate the contextually relevant risk and resilience factors for ADU.** Late adolescence and early adulthood are also when depression and other common mental health problems first emerge yet majority of prior studies typically focus on younger adolescents. Most of the prior studies are constrained by the small samples of AYLHIV who report ADU. In this proposal, we focus on AYLHIV in fishing communities – vulnerable communities that have high rates of HIV and drug use. Together, this approach will ensure that we have a large sample size of AYLHIV reporting ADU, to explore the risk and resilience factors and their potential interactions. Such knowledge is necessary to develop effective interventions to prevent/reduce ADU among AYLHIV. (2) **Our intervention targets the most commonly occurring risk factors for ADU (i.e. poverty and mental health problems).** Only a few ADU interventions evaluated in SSA have targeted the family context. No study has targeted poverty and its attendant impacts (e.g. mental health) as a risk factor for ADU. In this proposal, we will examine the feasibility, acceptability and short-term effects of a family-based economic empowerment intervention to reduce/prevent risky and hazardous alcohol drinking and drug use. The proposed FEE intervention is based on Asset theory and is intended to improve economic wellbeing and create a more hopeful/optimistic outlook for the future, and thus reduce AYLHIV's engagement in risk-taking behaviors including alcohol and drug use. This will be one of the first studies to examine the impact of FEE interventions on reducing alcohol/drug use among AYLHIV in poverty-impacted communities. (3) **We utilize biological measures to address limitations of self-reported drug use.** Self-reported measures are frequently used to assess ADU yet, due to a number of factors including the legal drinking age, gender, religious practices, social/cultural acceptability around alcohol use, recall and social desirability bias, these measures result in significant under-reporting of ADU. In addition, in SSA including Uganda, a substantial proportion of all alcohol consumed (~40% in LMICs and ~89% in Uganda) is homemade, which makes it difficult to determine the quantity of alcohol consumed. Hence, the inclusion of biological measures for ADU (urine test) can overcome

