
## C.2. Research design and study sites.

We propose a mixed-methods study comprising 4 components: (1) focus group discussions (FGDs) with AYLHIV (n=20) and in-depth qualitative interviews (QI) with health providers (n=10). AYLHIV will be recruited from two randomly selected clinics; 10 participants per FGD; (2) a cross-sectional survey (CS) with 200 AYLHIV; (3) a randomized control trial (RCT) with a sub-group of AYLHIV (n=100); and (4) two post-intervention FGD with AYLHIV (n=10 per study group). The study will be conducted in six

randomly selected HIV clinics located in fishing districts within the Greater Masaka region of Southwestern Uganda- a region heavily affected by HIV (12% prevalence vs. 6.2% national average) with high rates of household poverty and alcohol use. Urine tests for ADU will be conducted among all 200 AYLHIV who participate in the cross-sectional survey and among the 100 who participate in the RCT at the two time points. However, given the minimum and maximum detection times for different drugs of abuse in the urine, we will not exclude those with a positive self-report but negative urine test results from being included in the RCT. Additional analyses will explore the association between self-reported use and biomarkers.

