## C.3. Inclusion criteria.

The target populations for this study are: 1) AYLHIV, 2) healthcare providers at the selected HIV clinics. All study participants will be recruited from the selected HIV clinics. **Inclusion criteria for clinics:** 1) located in the - fishing districts with known HIV hotspots (i.e. 2 randomly selected clinics per district); 2) accredited by the Uganda Ministry of Health as a provider of ART; 3) currently have established services for AYLHIV. **Inclusion criteria for AYLHIV:** 1) male or female AYLHIV aged 18-24 years 2) medically diagnosed with HIV and aware of their HIV status; 3) enrolled in care at one of the selected HIV clinics. **Inclusion criteria for health providers:** health providers (1 - 2 per clinic) will be recruited from each of the selected clinics. **Inclusion criteria for participants of the RCT:** a sub-sample of AYLHIV (n=100) with a positive self-report for ADU will be randomly selected and randomly assigned at the clinic level (3 clinics per group) to either an intervention group (n=50) or a control group (n=50). AYLHIV from the control (n=10) and intervention groups (n=10) will participate in two FGDs at the end of the intervention.

**Exclusion criteria for RCT and post-intervention FGD:** any AYLHIV with negative self-report for ADU. **Exclusion criteria for all participants:** anyone with a significant cognitive impairment that interferes with their understanding of the informed consent process, or who is unable/unwilling to consent.

Table 1.

SOCIO-ECOLOGICAL FRAMEWORK		Time collected
Level	Risk/protective factor	
Individual	Socio-demographic: Gender; Age; orphanhood; education, income and unemployment; food insecurity  ; experienced homelessness; refugee; day/boarding school; urban/rural residence. Mental health: Depression,  hopelessness,  Optimism  ; Stress,  pain,  history of substance abuse 	CS, QI, FGD, RCT
Interpersonal/ Relationship	Loneliness  ; number of close friends; bullying; interpersonal violence;  social support  ; family cohesion  ; childhood abuse/trauma;  family history of substance abuse,  sexual risk-taking 	
Community	Community norms; access to alcohol and illegal drugs	
Society	Educational campaigns; price and supply of alcohol, social stigma 	

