
#### C.7.1 Quantitative Data analysis.

**Analysis of cross-sectional survey data:** Frequency distributions and summary statistics for the outcome and all predictor variables will be derived. The prevalence of ADU from both biological tests and self-reports, assessed using the Smoking and Substance Involvement Screening Test (NIDA-Modified ASSIST) among AYLHIV, will be calculated by dividing the number who tested positive for ADU by the total number of participants tested, and dividing the number screened to be of moderate or high risk in self-reported data by the total number of participants who completed the survey. To determine which multilevel factors are associated with substance misuse, we will fit logistic regression models comprising the outcome (ADU) and potential risk factors with standard errors adjusted for clustering by clinics.

**Analysis of RCT data:** Primary hypothesis. We hypothesize that participants in the intervention group will have a lower odds of ADU compared to participants in the control group. To test this hypothesis, we will fit three-level mixed-effects models. Each model will comprise the outcome, and fixed categorical effects for study group (intervention vs control), time (baseline, 6-months), and a group-by-time interaction term. Random intercepts will be fitted at the clinic and person level, with unstructured correlations among subjects' repeated measures. Robust Huber-White standard errors and test statistics will be computed for each model. We will assess the omnibus effects for study group, time, and their interaction. Post-estimation analyses will be conducted to assess time-within group simple effects and group within time simple effects. Secondary hypothesis. We hypothesize that AYLHIV in the intervention group will have better mental health outcomes including lower levels of

depressive symptoms, less hopelessness, improved adherence and achieve better viral suppression and improved economic outcomes than AYLHIV in the control group.

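### The survey risk-factor regression has about 31 candidate factors and perhaps 40 to 100 positives, with no limit on terms, no penalisation and no multiplicity rule

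*Protocol*

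**What the plan says.** Protocol C.2 plans "2) a cross-sectional survey (CS) with 200 AYLHIV". For Aim 1b, C.7.1 states that "we will fit logistic regression models comprising the outcome (ADU) and potential risk factors with standard errors adjusted for clustering by clinics". It does not say which factors enter, whether they enter together or one at a time, how terms are selected, or how multiple tests are handled.

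The candidates are in Table 1 (section C.3). They run from individual items such as "orphanhood; education, income and unemployment; food insecurity", through interpersonal ones such as "number of close friends; bullying; interpersonal violence", to "Community norms; access to alcohol and illegal drugs" and "Educational campaigns; price and supply of alcohol, social stigma". Under C.5 the qualitative phase feeds into the survey questions, so the list may grow.

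Section B says the choice of population will secure "a large sample size of AYLHIV reporting ADU, to explore the risk and resilience factors and their potential interactions". No expected number of positives, power or precision is given for the survey. The SAP does not mention this regression; its caution about small samples concerns the pilot RCT.

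**The concern.** The information in a logistic regression depends on the smaller outcome group, not on the 200 people surveyed. With few positives per term, maximum-likelihood coefficients are biased away from zero and Wald tests reject too often. Clinic-adjusted standard errors do not remove the first problem. With only six clinics they worsen the second if a normal reference is used.

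Aim 1b is meant to identify the factors behind ADU, and the study objectives say the findings will inform prevention work and, if warranted, an R01 application. An analysis that overstates real associations and adds a few false ones would carry those errors forward. Leaving the choice between joint and separate models open until the data are seen adds a further way to be misled.

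**Working it through.** The documents give no events, power or precision figure for the survey, so there is none to reproduce.

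**Inputs**
- Participants: 200 (C.2), from six clinics (C.4).
- Factors, counted from Table 1: 11 socio-demographic + 6 mental health + 9 interpersonal + 2 community + 3 society = 31. It is 30 without the participant's own substance history, and 32 if price and supply are separated.
- Positives: not stated. A.1 reports that over 30% of Ugandan adolescents and youth have used alcohol "and about 20% misuse alcohol": 0.20 × 200 = 40. Its 34.1% for alcohol use at ages 20-24 in sub-Saharan Africa gives 0.341 × 200 = 68. C.6 draws 100 ADU-positive RCT participants using the survey data, which implies about 100.
- Significance level: not stated; two-sided 0.05 assumed.
- Effect sizes and correlations: not in the documents; assumed below.

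**Events per factor, if all are fitted together**

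40/31 = 1.3; 68/31 = 2.2; 100/31 = 3.2.

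**Joint maximum-likelihood fit, simulated** (n = 200, 31 factors, pairwise correlation 0.2, five true odds ratios of 1.5, 26 null factors, model-based standard errors, 1,500 runs)

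| Prevalence | Mean log-OR inflation | OR scale | False factors of 26 | Chance of at least one |
|---|---|---|---|---|
| 20% | 40% | 1.5^0.40 = 1.18 | 2.1 | 84% |
| 34% | 29% | 1.5^0.29 = 1.12 | 2.0 | 84% |
| 50% | 27% | 1.5^0.27 = 1.12 | 1.9 | 82% |

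Repeat runs under the same assumptions put the log-OR inflation between 24% and 41%: 1.5^0.24 = 1.10 and 1.5^0.41 = 1.18, so 10-18% on the OR scale. Of the two or so false factors, 26 × 0.05 = 1.3 is nominal error.

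The size depends on the assumptions. With uncorrelated factors, OR-scale inflation (median or geometric mean) is 9-15% for a true OR of 1.5 and 15-42% for 2.0, across 40 to 100 events. With correlation 0.3 and OR 2.0 it is 26-30% at 100 events and 56-88% at 40.

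**Six-clinic robust standard errors**

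On a normal reference, about four of the 26 null factors are significant. On t with 5 degrees of freedom, it is about two. With all 31 factors null, the counts are 4.0-4.3 (normal reference), 2.0-2.1 (t(5)) and 2.2-2.3 (model-based).

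**Factors fitted one at a time** (all null and independent, tests at nominal level)

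Expected false factors: 31 × 0.05 = 1.55. Chance of at least one: 1 − 0.95^31 = 0.796.

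**Interaction between two balanced binary factors** (four cells of 50, prevalence p)

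SE = √(4 / (50·p·(1 − p))). Ratio of ORs detectable with 80% power = exp(2.80 × SE).
- p = 0.20: SE = 0.707, ratio 7.2
- p = 0.34: SE = 0.597, ratio 5.3
- p = 0.50: SE = 0.566, ratio 4.9

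Simulated power for a ratio of 2 is 15%, 20% and 23% respectively.

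**Effect of changing the method**

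Firth-penalised fitting of the same 31 factors cut the log-OR inflation to about 2% or less, and false factors to about 1.1. Separately, an ordinary fit of 10 factors (five true, OR 2.0, uncorrelated) had OR inflation of 5-8%.

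**The case against.** The strongest reply is that Table 1 is a data-collection framework, not a model specification. C.7.1 speaks of models in the plural and never says that all factors enter together. This stands. A reader might infer that the protocol commits to one 31-term model; it does not. If factors are fitted singly, the inflation argument largely drops out, but the multiplicity problem remains.

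Second, a reader might take the A.1 rates as planning figures and expect only 40 to 68 positives. They are background rates for alcohol in other populations. A.1 says rates are higher in fishing villages, and C.6 implies about 100. The regression outcome could still be rarer than RCT eligibility, since C.7.1 counts self-reported prevalence only at moderate or high risk. Hence the range of 40 to 100.

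Third, a reader might carry the 24-41% over to the odds ratios themselves. It is on the log scale, and the documents supply no effect sizes or correlations that would fix a single value on either scale.

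Fourth, section B contrasts the sample with earlier studies that had few ADU reporters, and it says only that interactions will be explored. It promises no power, so it should not be read as a failed power claim. What stands is that interactions are poorly supported even at the favourable end.

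**Conclusion.** The concern holds in a limited form. Nothing in either document restrains about 31 candidate factors on about 40 to 100 positives. A joint fit would have 1.3 to 3.2 events per factor, with mean log-OR inflation of about 24-41% (10-18% on the OR scale) under five true ORs of 1.5 and correlation 0.2. About two null factors of 26 would appear significant, or about four if the planned clinic-robust tests use a normal reference. Separate fits exchange the inflation for 1.55 expected false factors and about an 80% chance of at least one, if all are null and independent. Interactions need a ratio of ORs of about 5 or more for 80% power.

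The direction of the bias and the low event count hold across the whole range of positives. The percentages rest on the stated assumptions.

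**What to change.** In C.7.1, or in a survey section added to the SAP:

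- Name a short primary set of factors before analysis, sized to the observed number of positives, and state which ADU definition is the outcome.
- Fit any multivariable model by Firth or ridge-penalised logistic regression, and say how clinic clustering is carried into that fit.
- Refer clinic-clustered tests to a small-sample distribution such as t with 5 degrees of freedom.
- Report the remaining Table 1 factors as exploratory, with a false-discovery-rate adjustment.
- In section B, describe interaction analyses as hypothesis-generating, with about 40 to 100 positives expected.

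The timeline places the survey analysis in December 2022 to January 2023. If it has already been run, the short set should be labelled as chosen afterwards; the other changes still apply.

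The cost is wording and standard software, with no change to data collection. Fewer factors carry a headline result, and the estimates are slightly more conservative.

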### **C.7.2. Qualitative data analysis**

Interviews will be transcribed and uploaded to QSR NVivo12. Analytic induction techniques will be used for coding. Ten interview transcripts will be randomly selected, read multiple times and independently coded by the team using sensitizing concepts to identify emergent themes (open coding). Broader themes will be broken down into smaller, more specific units until no further subcategory is necessary. Analytic memos will be written to further develop categories, themes, and subthemes, and to integrate the ideas that emerge from the data. Codes and the inclusion/exclusion criteria for assigning codes will be discussed as a team to create the final codebook in NVivo. Each transcript will then be independently coded by two investigators using the codebook. Inter-coder reliability will be established. A level of agreement ranging from 66 to 97% based on level of coding indicates good reliability. Disagreements will be resolved through team discussions. The secondary analysis will compare/contrast themes and categories within and across groups to identify similarities, differences, and relationships among findings. Member checking, peer debriefing, and audit trail will be used to ensure rigor.

### **C.7.3. Data integration.**

The qualitative and quantitative data analyses will be done separately. Findings will be integrated at the interpretation and discussion stages. Conclusions and inferences will be synthesized for a more contextualized and thorough understanding of the multi-level factors associated with ADU among AYLHIV. The mixed methods design will serve two purposes: 1) Complementarity and 2) Expansion. Qualitative findings will be connected to quantitative findings where the former will provide explanations and context for findings produced by the latter. More specifically, the qualitative data will potentially provide further explanation and contextualization of the local factors that contribute to alcohol and drug abuse among AYLHIV in Uganda. The post-intervention FGDs with AYLHIV who participate in the RCT will explore participants' experiences with the intervention and share recommendations on how it can improve.

### **C.8. Potential challenges and alternative strategies.**

[figure not shown]
We do not anticipate major threats to study implementation but we recognize potential concerns. We plan to utilize recruitment strategies that have been successful in ICHAD's NIH funded studies. Should recruitment or enrollment deviate from anticipated rates, we will schedule conference calls to enact solutions and adjust the analytic strategy if necessary.

### **C.9. Dissemination.**

The research team will facilitate learning across stakeholders and maximize use of the evidence generated through dissemination meetings. Uganda's mental health policy recognizes the burden and impact of ADU on adolescents, their families and communities. If findings warrant, we will leverage these policy guidelines to maximize dissemination of study findings.

## **D. TIMELINE.**

First 4 months (April - July 2022) will be spent acquiring IRB, developing/pilot testing study guides and questionnaires, hiring and training project staff, recruiting clinics and selecting participants for the FGDs and QIs. In the next three months (August – October 2022), we will conduct the FGDs and QIs, analyze the transcripts, develop the survey questionnaire concurrently, and then conduct the survey from October and December 2022. Analysis of the quantitative survey will occur from December 2022 to January 2023. Concurrently (from January), we will work on refining the intervention manuals and start recruitment for the 100 participants of the intervention in February 2023. We will allow 8 months to implement the intervention (April– November 2023), giving enough time for follow-up 6 months later. We will conduct the post-intervention FGDs with AYLHIV in December 2023. The rest of the study period will be dedicated to data analysis, preparation of manuscripts, report writing and dissemination.

**Assessing the Feasibility of Economic Approaches to Prevent Substance Abuse Among
Adolescents**

NCT Number: NCT05597865

Statistical analysis plan updated June 20th 2025

The primary study outcomes were feasibility and acceptability of the research protocol, assessed using a mixed methods approach. Quantitatively, feasibility will be determined by the proportion of participants who enrolled in the intervention. Acceptability will be determined by measuring retention rates at 6 months, adherence to study procedures, intervention attendance and engagement. To assess whether participants adhered to and engaged in the intervention components we will report descriptive statistics to track the number and percentage of participants completing each intervention session, and the retention rate at the 6-month follow-up.

To examine short-term outcomes of the randomized controlled trial (RCT), with a focus on changes in prevalence of alcohol and drug use and psychosocial variables from baseline to 6-months. Categorical variables will be summarized using counts and percentages, and continuous outcomes will be summarized using means and standard deviation (SD) for the overall group and by study arm. Following noted experts and NIH guidance, we acknowledge that pilot RCT studies are too small to allow for sufficiently powered statistical tests or reliable effect size estimates to be determined or to conduct formal tests of clinical outcomes. In addition, attempting to obtain precise estimates of effect sizes cannot be statistically justified. Thus, in this pilot RCT we will focus on feasibility and acceptability of the protocol- design and adjustments necessary to maximize recruitment, retention, and quality assessment of outcomes in future studies.

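### Does the SAP's move from a tested hypothesis on alcohol and drug use to feasibility and descriptive reporting call for a change to the plan?

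*SAP*

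**What the plan says.** Protocol, section C.7.1 (analysis of RCT data), ranks the trial's hypotheses: "Primary hypothesis. We hypothesize that participants in the intervention group will have a lower odds of ADU compared to participants in the control group". The method follows: "To test this hypothesis, we will fit three-level mixed-effects models", with fixed effects for group, time and their interaction and random intercepts for clinic and person. On testing it says "We will assess the omnibus effects for study group, time, and their interaction", and then "Post-estimation analyses will be conducted to assess time-within group simple effects and group within time simple effects". Depressive symptoms, hopelessness, adherence, viral suppression and economic outcomes fall under a secondary hypothesis. C.7.1 contains no feasibility or acceptability analysis.

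The SAP is headed "Statistical analysis plan updated June 20th 2025". Its opening paragraph says "The primary study outcomes were feasibility and acceptability of the research protocol, assessed using a mixed methods approach", to be judged by enrolment, 6-month retention, attendance and engagement. Its second paragraph treats ADU as a short-term outcome: "Categorical variables will be summarized using counts and percentages", overall and by arm. The reason given is that "pilot RCT studies are too small to allow for sufficiently powered statistical tests or reliable effect size estimates to be determined", and it extends this to formal testing of clinical outcomes. It does not mention C.7.1, the ADU hypothesis or the mixed models.

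**The concern.** Taken literally, the two documents give an analyst opposite instructions: test ADU as the primary question, or describe it and test nothing. When a later plan removes a pre-specified primary test, a reader wants to know whether the choice was made without sight of the results by arm. The SAP does not say. It carries a version date but no account of what was updated, and that date falls after the protocol's planned end of follow-up.

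The stated reason does not settle the timing. A trial of 100 participants in six clinics, three per arm, was already the design in C.2, C.3 and C.6 when C.7.1 planned these tests. If a change of this kind followed an unfavourable ADU result, a planned primary test could go unreported and the reader would see only a feasibility study. That would be a selective-reporting problem even with every reported number correct.

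**Working it through.** There is no sample-size or power figure in either document to reproduce. The check is a comparison of the texts, a check of the dates, and a rough measure of what was given up.

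**1. What changed, item by item**

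| Item | Protocol | SAP |
|---|---|---|
| Labelled primary | ADU hypothesis (C.7.1) | Feasibility and acceptability |
| ADU analysis | Mixed models | Counts and percentages, overall and by arm |
| ADU tests per model | 3 omnibus effects and 2 families of simple effects | None |
| Feasibility | Title, A.1, Aim 2, section B | Primary |

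The protocol never lists primary outcomes; it names a primary hypothesis for the RCT data. Aim 2 puts feasibility first and short-term effects second, and the SAP's two paragraphs follow that order. So the ADU hypothesis loses its rank and its tests, while feasibility is not a new aim. The test count is per model: C.7.1 speaks of models in the plural, and ADU is measured by both self-report and urine, so no total is fixed.

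**2. Which document governs.** The SAP is later, marked as updated, and concludes from its size argument that the pilot will concentrate on feasibility and acceptability. It has no sentence superseding C.7.1, but an analyst holding both documents would follow the SAP.

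**3. Dates**
- 3 November 2022 to 3 November 2024 is 731 days. To 20 June 2025 is a further 229. Total 960 days; 960/30.4375 = 31.5 months.
- End of December 2023 (planned post-intervention focus groups, section D) to 20 June 2025 is 537 days, or 17.6 months.
- If section D is read as placing follow-up six months after November 2023 (end of May 2024), the gap is 385 days, or 12.6 months.

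These intervals date one version of the SAP against planned milestones. They do not date the decision, and the actual data dates are not given.

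**4. What the dropped tests could have shown.** Assumed inputs, since the documents give none: two-sided 5% level, control ADU p₁ of 50%, 70% or 80% at 6 months, intracluster correlation (ICC) 0, 0.01 or 0.05, no dropout. From C.6: 50 per arm and six clinics, so average clinic size m = 100/6 = 16.7.

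Design effect = 1 + (m − 1) × ICC. At ICC 0.05 this is 1 + 15.67 × 0.05 = 1.78, so effective n per arm = 50/1.78 = 28.0.

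Power = Φ{[d − 1.96√(2p̄(1−p̄)/n)] / √[(p₁(1−p₁) + p₂(1−p₂))/n]}, where d = p₁ − p₂ and p̄ is the mean of p₁ and p₂. For 70% v 50% with n = 50: (0.200 − 1.96 × 0.0980)/0.0959 = 0.083, giving 53%.

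| ICC | Effective n per arm | Power for 20 points (p₁ = 50 / 70 / 80%) | Difference detectable with 80% power, in points |
|---|---|---|---|
| 0 | 50.0 | 53 / 53 / 59% | 26.7 / 27.5 / 26.1 |
| 0.01 | 43.2 | 48 / 48 / 53% | 28.5 / 29.6 / 28.2 |
| 0.05 | 28.0 | 33 / 33 / 37% | 34.4 / 36.7 / 35.6 |

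This compares arms at 6 months and ignores any gain from the baseline measurement.

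Clinics were the unit of allocation, which adds a second limit. Six clinics split three and three give 6!/(3!3!) = 20 allocations. If allocation was unrestricted, the smallest two-sided p-value from an exact clinic-level test is 2/20 = 0.10. The SAP's view that the trial cannot support formal tests is borne out.

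**The case for a change.** The strongest case for a change is that a pre-specified primary test disappeared without acknowledgement, and that pilot size cannot explain when or why, because the size was the same when the test was written. The protocol's own contingency in C.8 ties a change of analysis to recruitment or enrolment going off course, and the SAP does not say that this happened. One dated paragraph would cost little.

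Part of this stands. The departure is unacknowledged and undated, and the size argument does not date it. A reader cannot exclude that results by arm had been seen.

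The rest is weaker. C.8 offers one contingency and does not rule out other reasons. The documents show no sight of data by arm: an updated SAP implies a previous version, which is not among them, and section D gives planned dates only. Reporting the C.7.1 tests selectively would require the sponsor to contradict its own SAP. What remains is a dropped test that goes unmentioned, and since C.7.1 is public, a reader can see that it was planned. The protocol is itself mixed on emphasis: section A.2 presents the study as chiefly about impact on ADU, while the title and Aim 2 lead with feasibility.

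**Conclusion.** No change to the plan follows. The SAP lowers the rank of the ADU hypothesis and drops its tests without saying so, but the plan it puts in place is a fair choice for 100 participants in six clinics. ADU is still summarised by arm, no efficacy claim is made, and the risk of a false one falls. The effect on any estimate is nil. A statement of departure would require no new data and no new analysis, so what is missing is disclosure, which an ordinary report of the results would supply when it accounts for departures from protocol.

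This rests on reading the later SAP as governing and on ADU being reported by arm as planned, whatever the result. The power range of 33% to 59% depends on assumed ADU rates, ICC and full follow-up, and the conclusion does not need it. The timing of the decision relative to the data remains unknown, and nothing here should be read as suggesting that it was driven by results.
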